4. STUDY DESIGN

4.1 Overall Design

ACTT-3 will evaluate the combination of subcutaneous interferon beta-1a and remdesivir compared to remdesivir plus placebo. Subjects will be assessed daily while hospitalized. If the subjects are discharged from the hospital, they will have a study visit at Days 15, 22, and 29. For discharged subjects, it is preferred that the Day 15 and 29 visits are in person to obtain safety laboratory tests and OP swab and blood (serum only) samples for secondary research as well as clinical outcome data. However, infection control or other restrictions may limit the ability of the subject to return to the clinic. In this case, these visits may be conducted by phone call, home visit or remote telehealth procedure as per institutional standards. If the Day 15 and 29 visits are conducted by phone or remotely, only clinical data will be obtained (i.e., no specimens collected). The Day 22 visit does not have laboratory tests or collection of samples and is conducted by phone

The primary outcome is time to recovery by Day 29. Recovery is defined by discharge from the hospital (i.e., ordinal scale categories 1 or 2) or subject is still hospitalized, but not requiring supplemental oxygen and no longer requires ongoing medical care (category 3). See table above in [Section 3](#) for more details.

4.2 Scientific Rationale for Study Design

As the study is a multicenter, multinational randomized controlled study, we will be able to acquire rigorous data about the safety and efficacy of investigational therapeutic agents for COVID-19 that will lead to generalizable evidence. Randomization is essential for establishing efficacy of these new therapeutic agents. Last, collecting clinical and virologic data on enrolled subjects using a standardized timeline and collection instruments should provide valuable information about the clinical course of and morbidities associated with COVID-19 in a diverse group of hospitalized adults.

The ACTT-3 design will specifically evaluate the contribution of interferon beta-1a antiviral and immunomodulatory effect in combination with remdesivir while the control arm will receive the monotherapy with remdesivir plus placebo.

4.3 Justification for Dose

4.3.1 Justification for Dose of Remdesivir

The dose of remdesivir used in this study will be the same dose used in ACTT-1 and ACTT-2 and that is available under the EUA, with updates on duration of therapy and dosing for patients with low eGFR to reflect the wording in the EUA. The duration of dosing may be adjusted by the site similar to what is described in the EUA. The maximum number of doses to be given during hospitalization is ten doses. This includes the loading dose and all maintenance doses given during the study and pre-study if applicable.

4.3.2 Justification for Dose of Subcutaneous Interferon beta-1a

We will be administering a subcutaneous 44 mcg dose of Rebif® (interferon beta-1a) every other day for 4 doses while a subject is hospitalized. This is the dose that has been used in other COVID-19 clinical trials including the World Health Organization's Solidarity Trial.

Interferon beta has a bioavailability of about 30% after subcutaneous or intramuscular administration, demonstrating peak serum concentrations within several hours of a dose (36). Serum levels of interferon beta-1a typically peak 3 to 15 hours after intramuscular administration. After injection, it is absorbed mainly in the lymphatics. Interferon beta is distributed throughout the body, and likely does not cross the blood-brain barrier. It is unclear whether interferon beta crosses the placenta. Interferon beta is excreted by hepatic and renal pathways. In healthy volunteers, a single subcutaneous injection of 60 mcg of Rebif® resulted in a peak serum concentration (C_{max}) of 5.1 ± 1.7 IU/mL (mean \pm SD), with a median time of peak serum concentration (T_{max}) of 16 hours. The serum elimination half-life ($t_{1/2}$) was 69 ± 37 hours.

Appendix C - ACTT-3: Remdesivir + Interferon Beta-1a

Following every other day subcutaneous injections, an increase in AUC of approximately 240% was observed, suggesting that accumulation of interferon beta-1a occurs after repeat administration. Total clearance is approximately 33-55 L/hours.

5. STUDY POPULATION

Male and non-pregnant female adults ≥ 18 years of age or older with COVID-19 and who meet all eligibility criteria will be enrolled at up to approximately 100 clinical trial sites globally. The target population should reflect the community at large. The estimated time from screening (Day -1 or Day 1) to end of study for an individual subject is approximately 29 days.

Subject Inclusion and Exclusion Criteria must be confirmed by any clinician named on the delegation log. If there is any uncertainty, the PI should make the decision on whether a potential subject is eligible for study enrollment. There is no exclusion for receipt of SARS-CoV-2 vaccine (experimental or licensed).

5.1 Inclusion Criteria

1. Admitted to a hospital with symptoms suggestive of COVID-19.
2. Subject (or legally authorized representative) provides informed consent prior to initiation of any study procedures.
3. Subject (or legally authorized representative) understands and agrees to comply with planned study procedures.
4. Male or non-pregnant female adults ≥ 18 years of age at time of enrollment.
5. Has laboratory-confirmed SARS-CoV-2 infection as determined by PCR or other commercial or public health assay (e.g., NAAT and antigen tests) in any respiratory specimen or saliva, as documented by either of the following:
 - PCR or other assay positive in sample collected < 72 hours prior to randomization; OR
 - PCR or other assay positive in sample collected ≥ 72 hours but < 7 days prior to randomization AND progressive disease suggestive of ongoing SARS-CoV-2 infection.

Note: if written documentation of the positive test result is not available at enrollment (e.g. report from other institution), the subject may be enrolled but the PCR should be repeated at the time of enrollment.
6. Illness of any duration, and at least one of the following:
 - Radiographic infiltrates by imaging (chest x-ray, CT scan, etc.), OR
 - $\text{SpO}_2 \leq 94\%$ on room air, OR
 - Requiring supplemental oxygen
7. Women of childbearing potential must agree to either abstinence or use at least one primary form of contraception not including hormonal contraception from the time of screening through Day 29.
8. Agrees to not participate in another clinical trial (both pharmacologic and other types of interventions) for the treatment of COVID-19 through Day 29.

5.2 Exclusion Criteria

1. Anticipated discharge from the hospital or transfer to another hospital which is not a study site within 72 hours.
2. Subject meets criteria for ordinal scale category 6 or 7 at the time of screening.
3. Subject has a positive test for influenza virus during this current hospital admission.
4. Subjects with an estimated glomerular filtration rate (eGFR) < 30 mL/min are excluded unless in the opinion of the PI, the potential benefit of receiving remdesivir outweighs the potential risk of study participation.
5. ALT or AST > 5 times the upper limits of normal.
6. Total white cell blood cell count (WBC) < 1500 cells/ μ L.
7. Platelet count < 50,000/ μ L.
8. History of chronic liver disease (e.g., jaundice, ascites, hepatic encephalopathy, history of bleeding esophageal or gastric varices). No laboratory testing is needed.
9. Pregnancy or breast feeding (lactating women who agree to discard breast milk from Day 1 until three weeks after the last study product is given are not excluded).
10. Allergy to any study medication including history of hypersensitivity to natural or recombinant interferon beta or human albumin.
11. Patient has a chronic or acute medical condition or is taking a medication that cannot be discontinued at enrollment, that in the judgement of the PI, places them at unacceptable risk for a poor clinical outcome if they were to participate in the study.
12. Received three or more doses of remdesivir, including the loading dose, outside of the study for COVID-19.
13. Received convalescent plasma or intravenous immunoglobulin [IVIg]) for the treatment of COVID-19.
14. Received any interferon product within two weeks of screening, either for the treatment of COVID-19 or for a chronic medical condition (e.g., multiple sclerosis, HCV infection)
15. Received any of the following in the two weeks prior to screening as treatment of COVID-19:
 - small molecule tyrosine kinase inhibitors (e.g. baricitinib, imatinib, gefitinib, acalabrutinib, etc.);
 - monoclonal antibodies targeting cytokines (e.g., TNF inhibitors, anti-interleukin-1 [IL-1], anti-IL-6 [tocilizumab or sarilumab], etc.);
 - monoclonal antibodies targeting T-cells or B-cells as treatment for COVID-19
16. Prior enrollment in ACTT-3

5.2.1 Exclusion of Specific Populations

Children and adolescents will not be included in this trial. Remdesivir has only been used in a small number of pediatric patients. Interferon beta-1a has not been studied in pediatric patients, and no formal trials of Rebif® have been conducted in children or adolescents. Initial information about the epidemiology of COVID-19 indicates that the overwhelming burden of severe disease occurs among older adults, especially those with comorbidities. Given significant gaps in knowledge in this population, and a low incidence of severe morbidity/ mortality in children, this research is not known to have the prospect of direct benefit to individual child subjects, and the risk/benefits do not warrant inclusion of this population into this trial at this time.

Appendix C - ACTT-3: Remdesivir + Interferon Beta-1a

In nonclinical reproductive toxicity studies, remdesivir demonstrated no adverse effect on embryo-fetal development when administered to pregnant animals. Embryonic toxicity was seen when remdesivir was initiated in female animals prior to mating and conception, but only at a systemically toxic dose. Remdesivir has not been studied in pregnant women. Toxicology studies in all tested animal species (rats, mice and monkeys) showed that subcutaneous interferon beta-1a was well tolerated both in single-dose and repeat-dose studies. Interferon beta-1a showed no evidence of mutagenicity or teratogenicity, however it may have abortifacient potential. Because the effects of the study products on the fetus and the pregnant woman are not fully known, pregnant women will not be eligible for the trial.

In animal studies, remdesivir metabolites have been detected in the nursing pups of mothers given remdesivir. It is not known whether remdesivir is secreted in human milk. Similar animal studies have not been conducted for Rebif® and it is not known whether subcutaneous interferon beta-1a is excreted in human milk. Because the effects of remdesivir and subcutaneous interferon beta-1a on the breastfeeding infant is not known, women who are breast feeding will not be eligible for the trial unless they agree to discard breast milk produced from Day 1 to three weeks after the last study product is given.

5.3 Inclusion of Vulnerable Subjects

Certain subjects are categorized as vulnerable populations and require special treatment with respect to safeguards of their well-being. For this clinical trial, examples include cognitively impaired or mentally disabled persons and intubated individuals who are sedated. When it is determined that a potential research subject is cognitively impaired, federal and institutional regulations permit researchers to obtain consent from a legally authorized representative (LAR). The study team will obtain consent from these vulnerable subjects using an IRB-approved protocol- specific process for consent using a LAR. For this clinical trial, we will not enroll prisoners or detainees as subjects.

For subjects for whom a LAR gave consent, during the course of the study, if the subject regains the capacity to consent, informed consent must be obtained from the subject and the subject offered the ability to leave the study if desired.

5.4 Lifestyle Considerations

During this study, subjects are asked to:

- Refrain from drinking alcohol through Day 15.
- Avoid getting pregnant during the study from Day 1 through Day 29.
- Agreed not to participate in another clinical trial for the treatment of COVID-19 or SARS-CoV-2. This includes interventional trials that evaluate treatment of SARS-CoV-2 infection as well as the disease pathogenesis (e.g., experimental treatment trials for the COVID-19-related thrombo-occlusive disease respiratory complications and dysregulated immune response to the virus). Co-enrollment for natural history studies of COVID-19 or studies of SARS-CoV-2 diagnostics are permitted; however, participation in both ACTT

and these studies can only occur if the recommended blood collection volumes are not exceeded.

5.5 Screen Failures

Following consent, after the screening evaluations have been completed, the investigator or designee is to review the inclusion/exclusion criteria and determine the subject's eligibility for the study. If there is any uncertainty, the PI should make the decision on whether a potential subject is eligible for study enrollment.

Only basic demographic information and the reason(s) for ineligibility will be collected on screen failures. Subjects who are found to be ineligible will be told the reason(s) for ineligibility.

Individuals who do not meet the criteria for participation in this study (screen failure) because of an abnormal laboratory finding may be rescreened once.

5.6 Strategies for Recruitment and Retention

5.6.1 Recruitment

It is anticipated that patients with COVID-19 will present for hospitalization to participating clinical trial sites, and that no external recruitment efforts towards potential subjects are needed. Recruitment efforts may also include dissemination of information about this trial to other medical professionals / hospitals. The IRB will approve the recruitment process and all materials provided prior to any recruitment to prospective subjects directly.

Screening will begin with a brief discussion with study staff. Some will be excluded based on demographic data and medical history (e.g., pregnant, < 18 years of age, chronic liver disease, etc.). Information about the study will be presented to potential subjects or LAR and questions will be asked to determine potential eligibility. Screening procedures can begin only after informed consent is obtained.

5.6.2 Retention

Retention of subjects is critical to the success of the trial since the primary endpoint is measured through Day 29 (+ 6-day window) and every effort should be made to retain subjects in the study. As such, after hospital discharge, subjects will be reminded of subsequent study visits and every effort will be made to accommodate the subject's schedule to facilitate follow-up within the specified visit window. However, there are many circumstances that impact a site's ability to obtain outcome information after discharge. For example, given the clinical course of COVID-19, a subject may be readmitted to another hospital after discharge and therefore be unavailable at Day 15 or Day 22. Even if a study visit is missed or study product is discontinued, every effort should be made to keep subjects in the study to monitor for safety, mortality and ordinal scale at Day 29. Subjects should not be withdrawn from the study because a site is unable to contact them for a follow-up visit.

Another common lost-to-follow-up scenario during ACTT-1, involved subjects (or their LARs) asking that the study products and blood draws be discontinued due to terminal illness. These subjects should also be encouraged to remain in study for the final Day 29 ordinal scale

Appendix C - ACTT-3: Remdesivir + Interferon Beta-1a

determination by chart review or phone call. To facilitate retention, follow-up visits may be conducted by phone, home visit or remote telehealth procedure as per institutional standards if in-person visits at the clinical site on Days 15 and 29 are not feasible. Day 22 visit is by phone call or remote telehealth procedure.

5.6.3 Compensation Plan for Subjects

Compensation, if any, will be determined locally and in accordance with local IRB requirements and approval.

5.6.4 Costs

There is no cost to subjects for the research tests, procedures/evaluations and study product while taking part in this trial. Procedures and treatment for clinical care including costs associated with hospital stay may be billed to the subject, subject's insurance or third party.

6. STUDY PRODUCT**6.1 Study Product(s) and Administration**

Subjects will be randomized into one of two arms (1:1).

| Arm 1 | Arm 2 |
|---|--------------------------------------|
| Interferon beta-1a SQ injection + remdesivir IV | Placebo SQ injection + remdesivir IV |

6.1.1 Study Product Description**Remdesivir component:**

Remdesivir is a single diastereomer monophosphoramidate prodrug designed for the intracellular delivery of a modified adenine nucleoside analog GS-441524. In addition to the active ingredient, the lyophilized and solution formulations of remdesivir contain the following inactive ingredients: water for injection, SBECD, and hydrochloric acid and/or sodium hydroxide.

Interferon beta-1a /Subcutaneous Placebo component:

Rebif®, an interferon beta-1a, is a purified 166 amino acid glycoprotein produced by recombinant DNA technology using genetically engineered Chinese Hamster Ovary cells into which the human interferon beta gene has been introduced. The amino acid sequence of Rebif® is identical to natural fibroblast derived human interferon beta.

Rebif® (interferon beta-1a) is formulated as a sterile solution in a prefilled syringe intended for subcutaneous injection. Each prefilled syringe contains 0.5 mL of Rebif®. Each 0.5 mL of Rebif® will contain 44 mcg of interferon beta-1a, 4 mg human albumin, USP; 27.3 mg mannitol, USP; 0.4 mg sodium acetate; and water for injection, USP.

- Matching empty syringes that will be filled with 0.5 mL 0.9% normal saline at each site pharmacy; OR
- Matching syringes prefilled with 0.5 mL 0.9% normal saline or 0.5 mL sterile water for injection.

6.1.2 Dosing and Administration

All subjects will receive remdesivir as a 200 mg intravenous (IV) loading dose on Day 1, followed by a 100 mg once-daily IV maintenance dose up to a 10-day total course while hospitalized. Enrollment may proceed for subjects who received one or two doses of remdesivir under EUA or similar mechanism prior to randomization. If subjects already received the loading dose, then start at 100 mg/day on Day 1. Any doses of remdesivir under an EUA (or similar mechanism) within 1 week of enrollment will be counted, so the maximum number of remdesivir doses given to a subject is 10 (i.e. EUA doses + doses on this trial). If one or two doses of remdesivir were administered (under EUA or similar mechanism) prior to study enrollment, this should be documented in eClinical as a concomitant medication given prior to Day 1.

For the subcutaneous interferon beta-1a / placebo component, subjects will receive either active product or placebo as follows:

- Interferon beta-1a will be administered every other day as a 44-microgram subcutaneous dose for a total of 4 doses while hospitalized
- A saline placebo will be administered every other day as a subcutaneous injection for a total of 4 doses while hospitalized

Study teams will instruct the administering nurse to use a different site for each subcutaneous injection. If there is an injection site reaction including skin that is irritated, edematous, reddened, bruised, or necrotic, the study product should not be administered into the affected area. If possible, select a unique site for each subsequent injection.

Dosing of the two medications does not need to occur at the same time.

Duration of therapy:

- IV remdesivir – up to 10 consecutive days while hospitalized (i.e., maximum of 10 total infusions pre-enrollment and during study).
- Subcutaneous (Interferon beta-1a or placebo) component – Days 1, 3, 5, and 7, while hospitalized.
- Both stop on discharge from hospital. If readmitted after discharge, see [Section 7.4](#).

6.1.3 Dose Escalation

Not Applicable

6.1.4 Dose Modifications

Appendix C - ACTT-3: Remdesivir + Interferon Beta-1a

The protocol-required safety laboratories (per the SOA) are anticipated to be sufficient for evaluating for dose modifications, but if other laboratory data obtained as part of standard care are available, these should also be used in the evaluation.

Remdesivir component:

The infusion should be held and not given if the subject is found to have any of the following laboratory values:

- eGFR decreases to < 20 mL/min
 - Remdesivir infusion will be held until the eGFR increases to a point that the potential benefit of giving remdesivir outweighs the potential risk. Note: this is consistent with the FDA Fact Sheet instructions for Health Care Providers, US EUA of Veklury® (remdesivir): "*Veklury is not recommended in adult patients with eGFR less than 30 mL/min...unless the potential benefit outweighs the potential risk*".
- ALT and/or AST increases to > 5 times upper limits of normal (ULN)
 - Remdesivir infusion will be held and not be restarted until the ALT and AST \leq 5 times ULN.

Interferon beta-1a /Subcutaneous Placebo component:

The subcutaneous injection should be held and not given if the subject is found to have any of the following laboratory values:

- ALT and/or AST increases to > 5 times ULN
 - Subcutaneous injection will be held and resume when ALT and AST \leq 5 times ULN.
- Total white cell blood cell count (WBC) <1000 cells/ μ L
 - Subcutaneous injection will be held and resume when WBC \geq 1000 cells/ μ L
- Platelet count <25,000/ μ L
 - Subcutaneous injection will be held and resume when platelet count \geq 25,000/ μ L.

Any dose that is held as described above, may be given later that day if the laboratory parameters improve. Any dose that is missed during the study due to any reason is not made up. The treatment course continues as described above even if the subject becomes PCR negative while hospitalized.

For laboratory values that meet permanent discontinuation thresholds (see [Section 7.1](#)), study product should be discontinued. However, if in the opinion of the investigator, the laboratory abnormality is due to intercurrent illness or another identified factor, laboratory tests may be repeated.

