2.2.2 Remdesivir

2.2.2.1 Potential Risks of Remdesivir

Remdesivir is not currently licensed in all countries where this study is conducted. In some countries where this study is conducted it is licensed, in some countries it is available under Emergency Use Authorization or conditional approvals, and in some countries, it is still considered an investigational therapeutic agent. As such, there are limited clinical data available for remdesivir.

Hypersensitivity reactions including infusion-related and anaphylactic reactions have been observed during and following administration of remdesivir. Signs and symptoms may include hypotension, tachycardia, bradycardia, dyspnea, wheezing, angioedema, rash, nausea, vomiting, diaphoresis, and shivering.

Asymptomatic transaminase elevations have been observed in healthy volunteers who received 200 mg of remdesivir followed by 100 mg doses for up to 10 days. Transaminase elevations have also been reported in patients with COVID-19 who received remdesivir in clinical trials. As transaminase elevations have been reported as a component of COVID-19, including in patients receiving placebo in clinical trials of remdesivir, discerning the contribution of remdesivir to transaminase elevations in this patient population is challenging. Preliminary data from a large randomized trial (ACTT-1) showed no differences in hepatotoxicity between the remdesivir and placebo arm.

In nonclinical animal studies, toxicity studies found dose-dependent and reversible kidney injury and dysfunction. In clinical studies, no evidence of nephrotoxicity has been observed with single doses of remdesivir up to 225 mg or multiple once daily doses of remdesivir 150 mg for up to 14 days. A 150-mg dose of the solution and lyophilized formulations of remdesivir contains 9 g and 4.5 g, respectively, of sulfobutylether-beta-cyclodextrin (SBECD), for which the maximum daily recommended daily dose (based on a European Medicines Agency (EMA) safety review) is approximately 250 mg/kg. Because SBECD is renally cleared, subjects with moderate or severe renal impairment may have SBECD exposures greater than those with less severe renal impairment or normal renal function. Based on this information, patients with an estimated glomerular filtration rate (eGFR) of less than 30 mL/min will be assessed by the PI and they will be eligible only if the benefit of participation outweighs the risk.

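### ACTT-3 applies a benefit-risk test for remdesivir below eGFR 30 mL/min at entry, but on study it sets no requirement for subjects who fall to 20-29 and no clear rule for those enrolled below 20

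*Protocol*

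**What the plan says.** All references are to Protocol Appendix C (ACTT-3) unless stated.

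- **Entry.** Exclusion 4, in the synopsis (1.1) and in 5.2: "Subjects with an estimated glomerular filtration rate (eGFR) < 30 mL/min are excluded unless in the opinion of the PI" finds a favourable benefit-risk balance for remdesivir. No lower limit is given. Section 2.2.2.1 gives the reason: the cyclodextrin vehicle is cleared by the kidney, so exposure may be greater with moderate or severe impairment. Hence "patients with an estimated glomerular filtration rate (eGFR) of less than 30 mL/min will be assessed by the PI".
- **Dose justification.** Section 4.3.1 says the regimen carries updates on "dosing for patients with low eGFR to reflect the wording in the EUA".
- **On-study hold.** Section 6.1.4 lists laboratory values at which the infusion is withheld. The renal one is "eGFR decreases to < 20 mL/min".
- **Restart.** The sub-bullet below it reads "Remdesivir infusion will be held until the eGFR increases to a point that the potential benefit of giving remdesivir outweighs the potential risk". Directly after that comes "Note: this is consistent with the FDA Fact Sheet instructions for Health Care Providers", followed by the quoted source: "Veklury is not recommended in adult patients with eGFR less than 30 mL/min", with an exception where the benefit-risk balance is favourable.
- **Other stopping rules.** Section 7.1.1 allows the investigator to stop dosing for severe laboratory abnormalities or in the subject's interest, and names no eGFR value. Section 7.1.1.1 refers back to 6.1.4 for laboratory-based changes and adds no renal criterion.

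**The concern.** The renal argument in 2.2.2.1 concerns exposure to the vehicle at reduced kidney function. It applies as much to a subject whose kidney function falls during treatment as to one who arrives with it reduced. The entry criterion and the quoted Fact Sheet sentence both place a benefit-risk judgement at 30 mL/min. The on-study rule has no counterpart until 20.

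Two things are at stake. First, section 4.3.1 presents low-eGFR dosing as following the EUA wording, so a site or ethics committee would take the condition to be in force throughout treatment. Followed as written, the rules do not require it at 20-29. Second, sites can read the rule for a subject enrolled below 20 in two ways, so the same subject might be treated at one site and held at another.

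This is mainly a matter of subject safety and uniform conduct. Both arms receive remdesivir and the injection is blinded, so uneven reading by sites is not in itself a mechanism that favours one arm. It would add noise to the listed safety endpoint on discontinuation or temporary suspension of study product.

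**Working it through.** No sample size, power or error rate is involved, so there is no figure to reproduce. The check sets the eGFR rules side by side and follows each kind of subject through them.

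| Rule | Section | eGFR line (mL/min) | What happens |
|---|---|---|---|
| Entry | 1.1 and 5.2, exclusion 4; 2.2.2.1 | < 30, no lower limit | Excluded unless the investigator's benefit-risk judgement is favourable |
| Dose justification | 4.3.1 | no number | Said to follow the EUA wording |
| On-study hold | 6.1.4 | < 20 | Infusion withheld |
| Restart after hold | 6.1.4 | no number; eGFR must rise | Benefit-risk judgement |
| Source quoted in 6.1.4 | 6.1.4 | < 30 | Not recommended unless benefit-risk is favourable |
| General discretion | 7.1.1 | none | Investigator may stop |

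The band between the entry line and the hold line is 30 - 20 = 10 mL/min, that is, 20 to below 30.

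1. **Enrolled at 30 or above, falls to 20-29.** Exclusion 4 is a screening criterion and was met. The hold in 6.1.4 is not triggered. The benefit-risk wording in 6.1.4 is not reached, because it sits in the restart sentence and needs a prior hold. Section 7.1.1.1 points back to 6.1.4, and 7.1.1 permits stopping without requiring an assessment. So dosing continues with no assessment required.
2. **Enrolled at 20-29 under the exception.** The investigator's assessment was made at entry. No gap arises from the band itself.
3. **Enrolled at 20 or above, falls below 20.** The infusion is held, and a benefit-risk judgement is needed to restart. If this subject recovers into the 20s, restarting takes an explicit judgement. The subject in step 1, at the same kidney function, needs none.
4. **Enrolled below 20 under the exception, for example at 18.** Exclusion 4 admits the subject because the balance of receiving remdesivir was judged favourable. The lead-in to the list in 6.1.4 turns on what value the subject is found to show, which would cover a value of 18. The bullet itself speaks of a decrease, which a subject who started at 18 has not had. If the hold applies, "Remdesivir infusion will be held until the eGFR increases to a point that the potential benefit of giving remdesivir outweighs the potential risk" asks for a rise in eGFR before a balance that was already judged favourable at 18 can count. If it does not apply, no hold value is stated for this subject. Note 4 to the Schedule of Assessments (1.2) lets the first dose go ahead without review of Day 1 results, so the question would arise from later doses on.

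As a comparison of structure only, Appendix D (ACTT-4) uses an investigator-judgement band of 15-30, excludes everyone below 15, holds remdesivir below 15, and asks for both eGFR of at least 15 and a favourable balance before resuming. Its entry floor equals its hold value, so the case in step 4 cannot arise there.

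**The case against.** The strongest defence is that this is a deliberate two-tier scheme: clinical judgement below 30 and an automatic hold at a lower value. That is coherent. Appendix D does the same, and within Appendix C the injection is held at lower white-cell and platelet counts (1000 and 25,000 per µL) than the entry limits (1500 and 50,000). A hold value below an entry limit is therefore not an error in itself. This part of the defence stands.

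A reader might infer four stronger things, and the documents do not support them.

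- *That 6.1.4 falsely declares its trigger of 20 to match a source that says 30.* The consistency note follows the restart sentence, whose benefit-risk wording does match the quoted source. It is not clearly a statement about the trigger. The source is an EUA Fact Sheet quoted with an omission, so only the quoted fragment can be compared.
- *That the quoted sentence forbids dosing below 30.* It is conditional and leaves room for a favourable judgement.
- *That everyone at 20-29 is dosed unassessed.* Subjects enrolled in that band were assessed at entry. For later decliners the assessment is not required, but it is not ruled out: 6.1.4 directs use of available routine laboratory data, and 7.1.1 allows stopping.
- *That entry and on-study rules give opposite instructions for the same kidney function.* They govern different moments. For a subject enrolled below 20, the wording of the trigger makes the position ambiguous. It is not a proven contradiction.

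The two-tier defence does not supply a rule for the upper tier on study. ACTT-3 never says that the judgement below 30 continues after entry, although 4.3.1 makes a general statement about low-eGFR dosing that is not confined to restarting.

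**Conclusion.** The point holds in limited form. For subjects who fall from 30 or above into 20-29 during treatment, nothing in Appendix C requires the benefit-risk assessment that exclusion 4 and the quoted Fact Sheet sentence apply below 30. The statement in 4.3.1 is wider than the rules that carry it out. For subjects enrolled below 20 under the exception, the appendix does not settle whether the hold applies.

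The extent is a 10 mL/min band for later decliners, plus anyone enrolled below 20. The documents give no count for either group, and the second could be empty. The conclusion rests on reading exclusion 4 as an entry criterion only and on the Fact Sheet text as quoted. It implies no view on which threshold is right. The instructions concern renal safety and sites can read them differently, so they should be amended, but nothing here undermines the trial's primary comparison.

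**What to change.** Reconcile exclusion 4 (1.1 and 5.2), 2.2.2.1, 4.3.1 and 6.1.4 of Appendix C. The sponsor and its clinical and regulatory advisers should decide the content. The text should then:

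- state what, if anything, is required when an enrolled subject's eGFR falls into 20-29;
- state what applies to a subject enrolled already below the hold value, either in the trigger wording of 6.1.4 or in exclusion 4;
- limit the consistency note in 6.1.4 and the EUA statement in 4.3.1 to what the rules deliver, and give the reason for any intended difference from the quoted sentence.

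The cost is a wording amendment and a note to sites. No new procedure is needed. Creatinine is already a scheduled safety laboratory test (Schedule of Assessments, note 6), and note 3 already asks each site to use one eGFR formula throughout. Note 3 describes the eGFR calculation under screening, so the amendment should say that it is also made from on-study creatinine.
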